1.0 Background

Aneurysmal subarachnoid hemorrhage affects 6-8/100,000 people every year⁴. In addition to the various medical comorbidities that accompany this disease, about 50% will experience angiographic narrowing of the cerebral arteries (radiographic vasospasm) and 20-30% will experience delayed ischemic neurologic deficit (DIND, formerly clinical vasospasm)¹. The onset of vasospasm is most commonly between days 4 and 14 after the hemorrhage. Patients afflicted with DIND may go on to suffer permanent neurologic deficits which can impair their quality of life or be fatal. Although there has been much advancement in the last 15-20 years in the ability to monitor and assess this condition, there has unfortunately been scarce progress in treating it effectively³.

The current mainstay of therapy is so-called hyperdynamic therapy, in which the patient's blood pressure is augmented and blood volume increased with the hope that resistance to flow can be overcome and the brain perfused². This comes with its own set of complications, such as cardiac injury and fluid overload. It is also important to note that this modality of therapy has never been validated in a randomized, controlled trial, though it is accepted as the standard of care in many institutions⁵. Patients that are refractory to medical therapy may undergo angiographic therapy with infusion of agents such as calcium-channel blockers or papaverine or in extreme cases, balloon angioplasty. Some groups, such as the Montreal Neurological Hospital, have used infusions of the drug milrinone (Hospira, Inc Lake Forest, IL) to counter cerebral vasospasm. The smooth muscle of cerebral blood vessels is rich in phosphodiesterase-III (PDE-III), making it a promising target for this drug⁶. Milrinone is currently FDA approved for the treatment of congestive heart failure as it has both vasodilatory and inotropic effects. It is thought that these same effects may be beneficial in cerebral vasospasm. Milrinone also has anti-inflammatory effects through inhibition of interleukins⁵.

Milrinone is known to be safe with a relatively low incidence of complications. The Montreal group had no patients (out of 88 presented) with complications from milrinone infusion for as long as 9 days. To date, no study has compared the current standard-of-care, hyperdynamic therapy, with milrinone in addition to standard treatment.

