4.0 Enrollment/Randomization

Location: IU Health Methodist Hospital, [name]

Process: Patients diagnosed with aneurysmal subarachnoid hemorrhage will be identified at the time of diagnosis and the research team will be contacted by the admitting team to monitor the patient. The patients will be consented and enrolled into the study as soon as possible following surgery or endovascular intervention, if the PI (or his assigned designee) determines the patient to meet all criteria other than evidence of vasospasm. A subject ID number, which is arbitrary, will be assigned to the patient once consented so that patient confidentiality may be protected. They will not, however, be randomized at this point. The patient's Legally Authorized Representative (LAR) will be contacted for consent if the patient is unable to provide it. If a LAR is not present at the bedside, initial contact may take place over the phone to establish a time to discuss the study and obtain consent in person. At the time of diagnosis of clinical vasospasm, the treating physician(s) will notify the research team. At this time, eligibility will again be reviewed with the PI (or his assigned designee) and the protocol orders will be signed and scanned to the pharmacy where they will be entered into CERNER and the pharmacy will randomize the patient to standard hyperdynamic therapy with placebo (normal saline) or standard therapy + milrinone. Randomization will take place at the time of protocol entry into CERNER. The diagnosis will be at the judgment of the treating physician and confirmed by the PI (or his assigned designee). Providers and patients will remain blinded to the drug. An index of which patients received the drug will be maintained by pharmacy services.

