8.0 Statistical Considerations

Sample size justification: Literature on the natural history and outcomes specifically of patients who suffer DIND is sparse. Based on our own experience, we expect to see mRS of 2 or less in approximately 50% of patients in the control group. With a sample size of 59 patients per group, the study will have 80% power to detect a 25% difference between the experimental and control groups (75% vs. 50% with mRS of 2 or less), assuming a two-sided chi-square test conducted at a 5% significance level.

The experimental and control groups will be compared for differences in baseline demographics and clinical characteristics using chi-square tests for categorical variables and Wilcoxon Rank Sum tests for ordinal and continuous variables. The primary outcome, mRS 2 or less at 6 months, will be compared between groups using chi-square tests. Secondary outcomes, including need for angiographic therapy, mRS 2 or less at 12 months, presence of side effects/complications, and discharge disposition will be compared between groups using chi-square tests, and mRS scores at 6 and 12 months, duration of vasospasm, and hospital and ICU lengths of stay will be compared between groups using Wilcoxon Rank Sum tests.

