Appendix A – Data Points for Milrinone Protocol

➤ **Demographics**

- Name
- DOB
- Age
- MRN
- Study ID#
- Gender
- Ethnicity
- Race

➤ **Past Medical History**

- HTN
- Smoker

➤ **Presentation/Pre-Intervention Data**

- Date of SAH symptom onset
- Date of hospital admission
- Time of hospital admission
- Hunt/Hess score on admission
- Fischer score on admission
- Location of aneurysm (side and vessel)
- Size of aneurysm
- # of aneurysms
- Modality of treatment indicated (clip/coil/both)
- Date of treatment procedure
- Time of treatment procedure

➤ **Post-Intervention Data**

- First date of elevated TCD
- Time of first elevated TCD
- Measurement of first elevated TCD
- Severity of spasm
- Mean TCD throughout hospitalization
- Max TCD throughout hospitalization
- Need for EVD
- Date of clinical diagnosis of vasospasm
- Time of clinical diagnosis of vasospasm
- Duration of spasm
- Date of end of spasm
- Evidence of ischemic changes on CT prior to study drug initiation (date/time)
- Evidence of ischemic changes on CT any time during hospitalization (date/time)
- Vasopressor usage
 - Drug(s) used
 - Duration of use

➤ **Study Drug Data**

- Date study drug initiated
- Time study drug initiated
- Duration of study drug exposure
- Study drug dose at initiation
- Was study drug titrated up?

- Hemodynamic parameters
- Creatinine clearance checked during current admission prior to study drug initiation
- Was study drug discontinued early due to complications?

➤ **Angiographic Therapy Data**

- Results of angiogram
- Severity of spasm on angiogram
- Intra-arterial drug use?
- Number of times angiographic therapy required

➤ **Complications**

- Hypotension
- Tachycardia
- Arrhythmias
- Chest pain
- Others at discretions of provider

➤ **Outcomes**

- Length of ICU stay
- Date of transfer to floor
- Date of discharge
- Length of hospital stay
- Discharge disposition
- Modified Rankin Score at 6 months
- Modified Rankin Score at 12 months
- Whether patient received milrinone or placebo

Figure 1

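### Hospital and ICU stay and vasopressor use are not anchored to randomisation, so they can take in days before any study drug was given

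*Combined protocol and SAP*

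**What the plan says.** - **When patients are randomised.** Section 4.0 takes consent after the aneurysm has been treated and adds: "They will not, however, be randomized at this point". The trigger comes later, when clinical vasospasm is diagnosed: "Randomization will take place at the time of protocol entry into CERNER". Section 1.0 gives the usual delay: "The onset of vasospasm is most commonly between days 4 and 14 after the hemorrhage". Section 3.1 excludes patients who arrive already in vasospasm.
- **Which measures are outcomes.** Section 2.0 names hospital stay, ICU stay and vasopressor usage as secondary outcomes. It does not name any TCD summary.
- **How they are analysed.** Section 8.0 says "duration of vasospasm, and hospital and ICU lengths of stay will be compared between groups using Wilcoxon Rank Sum tests". It gives no start point for either stay, and no test for vasopressor usage or TCD.
- **How they are recorded.** Appendix A lists both lengths of stay without a start point. It also collects the date and time of admission, the date and time of study-drug start, and the dates of floor transfer and discharge. Vasopressor usage is recorded as drugs and duration, with no dates, under the post-intervention heading. TCD is summarised by a mean and by "Max TCD throughout hospitalization". CT ischaemic change, by contrast, has two entries: one before study drug and one for the whole admission.

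**The concern.** A secondary outcome should measure what happens after the arms diverge. Here they diverge only when vasospasm is diagnosed, often days into the admission. A stay counted from admission is the sum of a part that treatment cannot alter and a part that it can. The unalterable part varies between patients and makes a real difference in stay harder to detect.

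Vasopressor duration raises a second problem. If the form does not say when counting begins, abstractors may choose different start points, and without dates the total cannot later be divided at study-drug start.

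The TCD summaries matter only if someone later uses them to describe drug effect. Raised velocity is one of the routes into the trial. For a patient who enters that way, the maximum over the admission cannot be lower than the qualifying reading, whatever the drug does.

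**Working it through.** **1. The plan's own figure.** Section 8.0 states "With a sample size of 59 patients per group, the study will have 80% power" for "75% vs. 50% with mRS of 2 or less", "assuming a two-sided chi-square test conducted at a 5% significance level". With pooled variance, p̄ = 0.625:

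n = [1.96·√(2·0.625·0.375) + 0.8416·√(0.25 + 0.1875)]² / 0.25² = (1.342 + 0.557)² / 0.0625 ≈ 57.7, so 58 per group.

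Power at 59 per group is 80.9%. The stated size reproduces. It concerns mRS only; the documents give no mean, SD or target difference for stay, vasopressors or TCD. The rest is therefore an illustration on stated assumptions.

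**2. Is there always pre-drug hospital time?** Yes. Exclusion of patients in vasospasm at arrival, together with randomisation at diagnosis, guarantees it. Its length is less certain: the 4 to 14 days in section 1.0 run from the haemorrhage, so the in-hospital part is shorter when admission is late.

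**3. Effect on the stay comparison.** Assumptions:
- post-randomisation stay is log-normal with mean 14 days
- milrinone shortens it by 20%
- there are 59 patients per arm and a two-sided Wilcoxon test at 5%
- pre-randomisation days are uniform and independent of later stay.

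A uniform 4 to 14 day window has SD 10/√12 = 2.89 days. Simulated power, 20,000 trials per row (simulation standard error at most √(0.25/20,000) = 0.35 points):

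| SD of post-randomisation stay | Counted from randomisation | Plus 4–14 earlier days | Plus 3–10 earlier days |
|---|---|---|---|
| 4 | 98.8% | 87.6% | 94.1% |
| 6 | 81.3% | 66.5% | 73.7% |
| 8 | 59.7% | 49.1% | 53.7% |
| 10 | 44.4% | 37.2% | 40.3% |
| 12 | 35.1% | 29.2% | 31.6% |
| 14 | 28.2% | 24.0% | 25.7% |

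The loss is 4 to 15 points with the longer window and about 2 to 8 points with the shorter one.

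**4. Cross-check by formula.** Choose the effect that gives 80% power when stay is counted from randomisation. Adding independent days with SD 2.89 gives, on the normal approximation,

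power = Φ(2.80·SD / √(SD² + 2.89²) − 1.96).

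For SD 5 this is Φ(2.80 × 5/5.77 − 1.96) = Φ(0.47) = 68%. For SDs of 3, 7 and 10 it is 52%, 74% and 77%. The loss shrinks as post-randomisation variation grows, as in the table.

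**5. Dilution of mean TCD.** Suppose readings are evenly spread over the stay and earlier days are uniform on 4 to 14. With L days after randomisation, the post-randomisation share of the averaging window is the mean of L/(L + earlier days). That is 45%, 54%, 62% and 71% for L = 7, 10, 14 and 21. An effect on post-drug mean velocity would shrink to about that fraction.

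**6. What can be recovered later.** Days from study-drug start to floor transfer and to discharge follow from listed dates. Vasopressor duration and the TCD mean and maximum cannot be split from the listed items, because no vasopressor dates and no serial TCD values are listed.

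**The case against.** The strongest reply is that this is a missing definition for secondary measures and not an error. Four parts of it stand.

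- A reader might infer that ICU stay and vasopressor use are counted from admission or from aneurysm repair. The documents do not say so; they are silent. For vasopressors the only hint is the form heading, which also covers the diagnosis and end of vasospasm and so groups fields without defining an analysis window. Section 5.1 describes vasopressors as part of the background therapy given alongside the infusion. It does not follow that perioperative use would be counted as an outcome.
- A reader might infer that the TCD summaries are planned efficacy outcomes that will be pulled towards no difference. They appear neither in the section 2.0 list nor among the section 8.0 tests. Entry may also rest on angiographic evidence, so not every patient has a qualifying velocity.
- A reader might infer that the comparison is biased. Pre-randomisation time is balanced in expectation by randomisation, and total stay from admission is a legitimate quantity to report.
- The size of the loss rests on assumed distributions. At large SDs it is only a few points, and the trial was not sized for stay.

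The reply does not remove the point. Stay is a tested secondary outcome, its ordinary reading starts at admission, and that reading gives a less precise comparison than the collected dates allow. For vasopressors, a listed outcome will be recorded in a form that cannot be repaired without returning to charts. The CT entries show that the plan already makes this kind of split elsewhere.

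**Conclusion.** The point holds as a matter of precision and definition. Hospital stay in its ordinary meaning includes time that study drug could not affect; ICU stay and vasopressor duration have no stated clock. With a mean post-randomisation stay of 14 days, a 20% shortening, 59 per arm and a 4 to 14 day window, the power loss for the stay comparison is roughly 4 to 15 points over SDs of 4 to 14 days, and less for a shorter window. All these inputs except the 59 and the 4 to 14 days are assumptions, as is independence of the earlier and later parts of the stay. The 4 to 14 days are themselves counted from haemorrhage.

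The documents do not support a claim of biased secondary results or of a flawed planned TCD analysis. The TCD summaries simply cannot serve cleanly as measures of drug effect as worded. The primary mRS outcome and the 59 per group are untouched. The change should be made, but the main conclusion of the trial does not depend on it.

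**What to change.** - **Section 8.0.** Define the tested stay outcomes as days from randomisation (or study-drug start) to floor transfer and to discharge. Report total stay from admission descriptively.
- **Appendix A, vasopressors.** Record use after study-drug start, with start and stop dates for each drug.
- **Appendix A, TCD.** Record the last reading before study drug as the baseline value, separately from the mean and maximum after study-drug start.

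For stay the cost is wording only, since the study-drug, floor-transfer and discharge dates are already collected. The small downside is a pre/post split of the vasopressor and TCD entries, which is best made at data collection because the listed items do not allow it afterwards.
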